### Evidence of Direct Benefit

We believe that this protocol is in the 405 risk category for pediatric research. Participants can benefit from the above study measurements.

Adolescents with severe obesity are at increased risk for diabetes, reduced exercise capacity, cardiovascular dysfunction, and increased visceral and liver fat. Therefore, obese non- severe obesity participants may benefit from the results of body composition, basal metabolic rate testing, MRI testing, glucose testing, insulin resistance assessment during baseline and 1-year post bariatric surgery. The metabolic cart testing can detect the basal metabolic rate, which can determine a personalized goal for target caloric intake following surgery. The MRI of the liver can detect early evidence of fatty liver disease or fibrosis. The blood tests done for screening can detect alterations in blood glucose and prediabetes. The risk of all of these endpoints is increased in sedentary participants, especially those who are also obese, and if left untreated can increase long term health risk, thus the benefit of detecting any of these would directly impact both the health and the longevity of the individual participant.

## **F. Alternative Treatment**

The alternative is for participants to not participate in the study

## **G. Consideration of Specific Participant Categories**

### **1. Inclusion of Women**

Every effort will be made to include a diverse gender distribution.

### **2. Inclusion of Minorities**

Every effort will be made to include a diverse participant distribution. Severe obesity affects Caucasians, Hispanics and African Americans equally.

### **3. Inclusion of Children**

All participants will be between ages 13 and 20. Insulin sensitivity needs to be studied in the adolescent age group as available is scarce in this age group and it is critical to understand the pathophysiology of NAFLD in its developing stages.

## **IV. Potential Scientific Problems:**

### **Limitation of Method Development:**

The protocol as described includes an OSTT with an oral tracer will be conducted in some of the participants. The specific points that are to be evaluated are listed below:

- 1) Measurement of Hepatic Substrate flux in youth during fasting.
  - a. Purpose: Asses hepatic substrate flux in youth looking at shifts from pentose phosphate pathway (PEP), TCA cycle and fatty acid synthesis
  - i. Rational: utilizing and oral glycerol model with NMR isotopomer analysis is a newer technique. We have validated the timing with an OSTT in youth. However, this relies on consistent OSTT responses, and in this study we will be using an MMTT. When we anticipate that the response to the MMTT may change pre/post surgery, and the timing and thus results would vary, and we are thus better off using a fasting model. This has been done in adults, but not in our youth.
  - ii. Measurement: NMR isotopomer analysis with pathway flux calculations and modeling in the fasting state
  - iii. Revision plan if model not correct: 1) increase the amount of tracer given 2) increase the frequency of blood draws in the later sampling period.

### **Overall Project Limitations:**

- 1) Participant recruitment is always a potential concern, but is minimized by a streamlined recruitment system and experience with this population; the previous, more intensive study is well tolerated in youth and enrolled faster than projected. The bariatric surgery clinic is becoming established, and referrals are increasing rapidly, now more than 10 a month. Of the surgeries completed in the last 5 months since the start of the clinic, 15 of the youth would have potentially qualified for this protocol.
- 2) Participant drop-out: We expect reasonably good completion rates due to the minimally-invasive nature of the study visits and our low dropout rate in our previous studies in control and severe obesity adolescents using similar procedures.
- 3) Underpowered: This is a pilot study and is likely underpowered to find associations between changes in metabolism and NAFLD status. However, the data generated from this protocol could then be used to apply for funding to continue the study in a larger cohort of youth, to fully answer some more of the mechanistic questions. If we can obtain additional funding we will revise the protocol to include more participants.

## **V. Data Management and Security Plan**

### **Data Entry**

Data will be entered from paper forms. Once forms are completed, verified and corrected for inconsistencies, they will be manually entered at our site using a computerized data management system (Redcap).

### **Edit Checks**

Computerized data validation routines will be used to enhance data quality and verify the accuracy of data within predefined value ranges. These checks include, but are not limited to: (a) initial screening of data, using logic and range checks built into data entry screens; (b) cross-form functional and consistency checks; and (c) edits assessing the serial integrity of data.

### **Disaster Recovery**

Routine data backup will occur on data in conjunction with the Children's Hospital secure server and Redcap.

### **Security and Confidentiality**

All hard copy forms will be de-identified with a study number and filed in a locked in a place in which only the investigators and qualified study team will have access. Standard protection against computer hackers is implemented. Recovery from natural disasters (water, fire, or electrical) can occur through the ability to reconstruct both the database management system and the data from nightly backups.

## **VI. Data and Safety Monitoring Plan**

The principal investigator and study coordinator will monitor the protocol and the safety of the research participants. The PI will review all laboratory data and report any abnormal values to the patient and guardian and instruct the participant to follow-up with their PCP. If an abnormal result from a research procedure exists, the PI will notify the family, the bariatric surgery team and their PCP and refer the participant to the appropriate clinic for further evaluation. The PI may also share research results in a reasonable and prudent manner with appropriate medical professionals if the participant was seriously injured as a result of a procedure or if follow-up of the result of the procedure is in the best interest of the participant's health as determined by a medical professional. If immediate medical follow-up of participant required, the PI will share the research results via EPIC when clinically relevant. The PI will report adverse events, and any decision to suspend or halt the protocol to CTRC and COMIRB immediately. The PI will also prepare a written report for the yearly continuing review required by COMIRB and the CTRC. There are no other entities that require notification about this protocol.

No protected health information will be collected until the appropriate HIPAA forms are completed. The protected health information that will be collected will include: Name and phone number, demographic information (DOB, sex, ethnicity, address, etc.), diagnosis(es), history and physical, laboratory or tissue studies, radiology studies, procedure results, survey/questionnaire results, research visit records, and portions of previous Medical Records that are relevant to this study. This information will be accessible only by the study investigators, Federal agencies overseeing human participant research, the Colorado Multiple Institutional Review Board, regulatory officials from the institution where the research is being conducted to monitor safety and compliance with policies.

### **A. Adverse Events (AE)**

The MMTT is a standard procedure used in a large number of research studies and settings. Adverse events are uncommon when the procedure is done by experienced personnel in an appropriate setting.

MRI procedures are considered safe as long as the participant does not have implanted metal. All participants undergoing screening by trained MR personnel prior to any scanning procedures.

### **1. Adverse Event Definition**

For the purposes of this study, an Adverse Event (AE) is defined as any significantly abnormal physical finding identified on examination and any significantly abnormal laboratory result obtained on the patient between visits or at the time of the visit. Questions answered YES and any new abnormal physical findings are pursued by the study staff in order to determine the seriousness of the event and the need for further evaluation, follow-up, or referral. If follow-up or referral of abnormal research results or procedure is required, the PI will place a referral in EPIC, update the PCP on patient condition and reason for referral and contact family to discuss follow-up treatment options.

#### **a) Adverse Event Reporting**

AEs are reported on a standard form that is completed by the study staff at each regular follow-up visit and phone interview. Adverse events reported or ascertained between clinic visits are captured and reported at the time of the next scheduled visit.

Pre-existing conditions (that is, conditions present prior to study enrollment) are not considered or recorded as AEs or SAEs unless the condition worsens in intensity or frequency after enrollment. Likewise, continuing adverse events are not reported as AEs at subsequent visits unless they increase in severity or frequency between the visits, they result in criteria for an SAE, and/or they resolve between visits.

### **B. Serious Adverse Events (SAE)**

#### **1. Serious Adverse Event Definition**

Events are divided into those that are not serious (AE) and those that are serious (SAE). The distinction between an SAE and an AE is a regulatory definition established by the FDA, not a clinical definition. The definition of SAE is not always related to clinical severity of the event. For the purposes of this study an AE is considered a Serious (SAE) when it satisfies any one of the following criteria:

- The event results in an inpatient hospitalization (any overnight stay associated with an admission).
- The event results in the prolongation of a hospital stay.
- The event results in permanent or severe disability.
- The event results in death.
- The event is life-threatening.
- Treatment is required to prevent a serious event.

There have been no SAE's in the research groups experience in the Pediatric CTRC. We do not anticipate encountering SAE's; however, we have identified the following as possible SAE's for the purposes of monitoring:

- Infection related to blood draw or IV placement

### **a) Serious Adverse Event Reporting**

Study patients are instructed to contact the clinic with any serious adverse event meeting the above criteria. Each SAE is recorded on the study form and the PI is informed as soon as possible after they occur and preferably within 24 hours of the notification of the clinic staff. This notification should occur even if data are incomplete. Additional data and follow-up information are documented and sent subsequently as an update to the original report. The PI immediately forwards SAE reports to COMIRB and any other required institutional monitoring committee.

### **C. Participant Discontinuation Criteria**

If a participant experiences any of the following, the participant will be withdrawn from the study.

1. Inability to complete study procedures
2. Abnormal clinical labs ( $\text{HbA1C} > 6.4\%$ ,  $\text{Hg} < 10 \text{ mg/dL}$ )
3. Participant becomes pregnant during study

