#### Exclusion Criteria:

1. Use of medications known to affect insulin sensitivity or hepatic outcomes: oral glucocorticoids within 10 days, atypical antipsychotics,

immunosuppressant agents, HIV medications, PPAR-γ or PPAR-α, metformin.

2. Infectious hepatitis
3. Alcohol abuse, (defined by the America Association for the Study of Liver Diseases as >21 drinks/week for males >14 drinks/week for females, with a drink considered 14 grams of alcohol)
4. Mitochondrial disease
5. Currently pregnant or breastfeeding women. Development of pregnancy during the study period will necessitate withdrawal from the study.
6. Severe illness requiring hospitalization within 60 days
7. Diabetes, defined as Hemoglobin A1C > 6.4%
8. Anemia, defined as Hemoglobin < 10 mg/dL
9. Diagnosed major psychiatric or developmental disorder limiting informed consent
10. Implanted metal devices that are not compatible with MRI

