#### **POST-SURGERY VISIT 3 (FIGURE 3: MMTT AND MRI):**

Same procedures as Baseline Visit will be repeated 1-year post-surgery (with exception of liver biopsy sample).

Figure 3: Post-Surgery Visit

Purpose for lab test to be drawn:

MMTT Labs	Purpose
Glucose	Determination of IR
Insulin	Determination IR and beta cell function
FFA	Measure of lipolysis
Glycerol	Measure of lipolysis
Glucagon	Gut hormone known to influence meal response glycemia
GLP-1	Gut hormone known to influence meal response glycemia
GGT	Marker of hepatic disease
C-peptide	Measure of beta cell function, insulin clearance
CMP	Markers of hepatic disease (Alk phos, ALT, AST, albumin)
Lipid panel	Markers of serum lipids, hepatic function
HbA1c	Long term marker of glycemia
Stored blood	Future markers of glucose and fat metabolism, CVD or hormones related to NAFLD
Isotopomer analysis	Hepatic mitochondrial function

Purpose for questionnaires being done:

Questionnaire	Description	Study Validity
Adolescent Sleep Hygiene Scale	Measurement of sleep patterns/habits	Cronbach's alpha ranges from .46-.74; total scale alpha = .80  LeBourgeois et al. 2005. The Relationship Between Reported Sleep Quality and Sleep Hygiene in Italian and American Adolescents
Center for Epidemiological Studies Depression (CES-D)	Measuring for depression	See Table 3 below, adapted from:  Stockings et al. 2015. Symptom screening scales for detecting major depressive disorder in children and adolescents: A systematic review and meta-analysis of reliability, validity and diagnostic utility
Cleveland Adolescent Sleepiness Questionnaire	Measurement of sleepiness during a typical week	alpha = .89  Spilsbury et al. 2007. The Cleveland Adolescent Sleepiness Questionnaire: A New Measure to Assess Excessive Daytime Sleepiness in Adolescents
SDQ: Strengths and Difficulties Questionnaire	Behavioral screening questionnaire	The internal reliability of the various self-report scales was assessed using Cronbach's alpha coefficient. This was 0.82 for the total difficulties, 0.75 for emotional symptoms, 0.72 for conduct problems, 0.69 for hyperactivity, 0.65 for prosocial behavior, and 0.61 for peer problems.  Goodman et al. 2003. The Strengths and Difficulties Questionnaire: a pilot study on the validity of the self-report version

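### The haemoglobin limit is written as 10 mg/dL and can never be met; in the same list, withdrawal for HbA1c above 6.4% has no time limit

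*Combined protocol and SAP*

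**What the plan says.** **Haemoglobin.** Exclusion criterion 8 in Section III.B reads "Anemia, defined as Hemoglobin < 10 mg/dL". Item 2 of Section VI.C, headed "Abnormal clinical labs", uses the same number and unit and abbreviates haemoglobin as Hg. The limit is not given in g/dL anywhere.

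**Withdrawal.** Section VI.C introduces its three items with "If a participant experiences any of the following, the participant will be withdrawn from the study". Item 1 is "Inability to complete study procedures". Item 2 combines HbA1c above 6.4% with the haemoglobin limit. Item 3 is "Participant becomes pregnant during study", the only one of the three with a time reference. The HbA1c limit is the one that exclusion criterion 7 uses at entry: "Diabetes, defined as Hemoglobin A1C > 6.4"%.

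**Context.** The primary outcome in Section III.A is the glucose and hormone response to a mixed meal. The calendar in Section III.C places that test at baseline, within two months before surgery, and again about one year after. HbA1c is in the table of MMTT laboratory tests. Section VI sets out a route for abnormal research results: tell the family, the surgical team and the primary care physician, and refer. The Data Analysis Plan (Section VII) does not say how withdrawn participants or missing values are handled.

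**The concern.** A threshold that decides who may enter and who must leave should be correct as written. This one is not, and it appears in a study of 13- to 20-year-olds that draws blood repeatedly during two meal tests and again during surgery. No other item in the eligibility or withdrawal lists deals with anaemia.

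The HbA1c item raises a different problem. HbA1c above 6.4% is the protocol's own definition of diabetes. At entry it defines the population. After surgery it becomes a result, closely related to what the primary outcome measures. A mandatory withdrawal rule without a time window, read literally, lets a post-surgery glycaemic result decide who stays in a before-and-after comparison.

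**Working it through.** **1. Unit conversion.**
- Input: limit of 10 mg/dL (exclusion criterion 8; Section VI.C item 2).
- 1 g = 1000 mg, so 10 mg/dL = 10 / 1000 = 0.01 g/dL.
- If 10 g/dL was meant, that is 10 × 1000 = 10,000 mg/dL.
- Ratio of intended to written limit: 10,000 / 10 = 1000.

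The limit is a stated threshold, not a derived figure, so there is no calculation of the plan's own to reproduce. The same unit stands in two separate sections, which makes a reading error in the PDF text an unlikely explanation.

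**2. Blood sampling that the limit bears on.**
- Section VII lists 12 sampling times per meal test (-10, 0, 10, 20, 30, 45, 60, 90, 120, 150, 180 and 240 min). Two visits give 12 × 2 = 24.
- The note on the day of surgery adds about 7 teaspoons: 7 × 4.93 mL = 34.5 mL.
- Section III.D item 1 separately states that the MMTT visit stays within blood-volume guidelines of 9 ml/kg in 6-8 weeks and 5 ml/kg.

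**3. When does the HbA1c item apply?** The text points both ways.
- *Towards a late eligibility check only:* the limits in item 2 match exclusion criteria 7 and 8, and neither the calendar nor the Screening Visit text lists a blood draw at screening. On that reading, item 2 catches people found ineligible once baseline results arrive.
- *Towards the whole study:* the Evidence of Direct Benefit text says "The blood tests done for screening can detect alterations in blood glucose and prediabetes", which implies that a screening draw already exists. Item 3 of the same list expressly runs during the study.

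The documents do not settle it.

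**4. What could be lost on the literal reading?** The only scheduled post-surgery HbA1c is at the one-year visit, which is the last. No later study visit remains to be missed. Loss would therefore need one of two things: an unscheduled clinical HbA1c above 6.4% between surgery and one year, or a decision to discard data already collected. No section states the second. The documents give no rate for the first. For scale only, one lost pair among the 16 participants that Section III.B aims to enrol is 1 / 16 = 6.25% of the sample. The number of such losses cannot be derived and may be zero.

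**The case against.** The strongest reply is that neither point will change what happens in practice. Clinical staff would very probably read the haemoglobin limit as g/dL, and blood-volume limits protect participants at the meal test independently. The HbA1c item can reasonably be read as a late eligibility check, and even on the literal reading the only scheduled measurement comes when all study data are in hand. All of this stands, and it is why the point is minor. It does not make the written limit correct, nor does it supply the missing time window.

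Three stronger readings are tempting, and the documents do not support them.

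- *That haemoglobin has no source in the study.* The MMTT laboratory table has no haemoglobin row; the metabolic panel row, for instance, reads "Markers of hepatic disease (Alk phos, ALT, AST, albumin"). But item 2 refers to clinical laboratory results, the Screening Visit relies on chart review, and the visit figures are not shown. Silence in one table does not establish that no value is available.
- *That one untolerated scan means withdrawal and biases the result.* Item 1 does lack detail. However, Section III.D says an intolerable scan is stopped and does not mention withdrawal. The calendar makes the glycerol drink optional and lets the MRI be done on another day, and the MRI and meal test are paid for separately. These point to partial completion being acceptable. Nothing links claustrophobia to glycaemic response, so no direction of bias can be claimed. The MRI is also needed for the hepatic-fat analysis under Aim 1, so it is not peripheral to the study.
- *That the HbA1c rule demonstrably flatters surgery.* Any figure for this would rest wholly on assumed HbA1c distributions and on an assumed link between HbA1c and the meal response. The documents give neither.

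**Conclusion.** The haemoglobin limit is wrong as written in both places, by a factor of 1000 on the assumption that g/dL was intended. As it stands, the only anaemia rule in the eligibility and withdrawal criteria cannot operate. This conclusion is certain from the text; the practical risk is small, so the severity is minor.

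The HbA1c item is a secondary point of wording. Withdrawal is mandatory, no time window is given, and after surgery the trigger is close to the primary outcome. Whether anyone would be lost depends on how the rule is read and on unscheduled testing. Its effect cannot be quantified from the documents and may be zero.

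**What to change.** - In exclusion criterion 8 and Section VI.C item 2, write Hb < 10 g/dL, replacing both the unit and the abbreviation Hg, after checking the unit in which the laboratory reports.
- In Section VI.C, state that the HbA1c limit applies only up to surgery. After surgery, the participant and all collected data are kept. A value above 6.4% is handled by the notification and referral route already in Section VI, and any glucose-lowering drug started is recorded.
- Otherwise leave the haemoglobin withdrawal rule as a safety rule. The pregnancy item needs no change.

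The cost is one short amendment to two lists, with no extra visits, tests or staff. The one small burden is that participants who start glucose-lowering treatment must be identified when the one-year results are read. This matters because metformin, for example, is an exclusion at entry.

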### **D. Protocol Stopping Criteria**

If one or more participants experience any of the SAE's listed above, the PI will consult with the study staff prior to continuing study visits with participants. The PI and RSA will consult about the significance of the SAE's and make a recommendation about participant continuation in the study.

## **VII. Data Analysis Plan:**

Mathematical plans:

**MMTT:** The metabolic response to the MMTT will be measured for 4 hours. Blood will be collected for glucose, insulin, C-peptide, GLP-1 and glucagon at -10, 0, 10, 20, 30, 45, 60, 90, 120, 150, 180 and 240 min after the start of the liquid meal ingestion.  $\beta$ -cell function will be quantitated by mathematical modeling of the plasma C-peptide response to the MMTT. The MMTT allows for calculating an estimate of the principal parameters of  $\beta$ -cell function after a physiological stimulus and is better tolerated than oral glucose post-bariatric surgery. The main parameter of the model is  $\beta$ -cell glucose sensitivity ( $\beta$ -GS), which is calculated as the mean slope of the dose-response function (i.e., the relationship between insulin secretion and plasma glucose concentrations during corresponding times of the MMT). The model also yields a measure of total insulin release over the 3 hr. Intestinal GLP-1 and  $\alpha$ -cell glucagon peak responses and area under the curve will also be calculated. The primary model outcome is  $\beta$ -cell glucose sensitivity ( $\beta$ -GS), a measure of  $\beta$  cell function calculated as the mean slope of the dose-response function i.e., relationship between insulin secretion rates and glucose concentration during the MMTT. The model also provides an estimate of glucose rate sensitivity (insulin secretory response to rate of change in glucose), and total insulin output (total amount of insulin released over the 4 h of the MMTT). The metabolic response to the MMTT can also be calculated using the using the trapezoid method for plasma glucose, insulin, and C-peptide AUCs.

